11.4.1. Types of Surgical Procedures

Open, laparoscopic, or thoracoscopic surgical procedures may include the following surgical specialties:

- General
- Gynecological
- Cardiothoracic.

Examples of types of surgical procedures considered for this study may include, but are not limited to:

Colectomy

Confidential Page 55 of 86

ETHICON, LLC. BIOS_2017_02

03 SEP 2019, VERSION: 1.1

- Low anterior resections
- Retroperitoneal tumor resection
- Liver resection
- Soft tissue bleeding after adhesiolysis
- Hernia repair
- Radical hysterectomy
- Lymphadenectomy
- Tumor removal surgery
- Diffuse bleeding on visceral or parietal pleura
- Soft tissue in cardiothoracic procedures.

11.4.2. Definition of Target Bleeding Site

The TBS will be defined as the first accessible bleeding site identified during dissection, related to the primary operative procedure requiring an adjunctive hemostat.

Once the TBS is identified and conventional techniques were considered impractical or ineffective, the surgeon will apply the randomized treatment at the TBS to cover the entire bleeding area. The bleeding severity will describe the intensity of the bleeding that is present at the time the surgeon determines that an adjunctive hemostatic product is required. At each investigational site enrollment will be stratified into two groups, according to TBS bleeding severity (mild or moderate bleeding).

As a frame of reference, only target bleeding sites with mild or moderate bleeding as defined by the following scale of bleeding intensity will be included:

Mild Bleeding: A TBS with a small area of capillary, arteriole, or venule oozing.

Moderate Bleeding:

1. A TBS with a larger area of capillary, arteriole, or venule oozing that presents a significant challenge because of the larger area involved, increasing the volume of blood loss.

or

2. A TBS with bleeding that is more pronounced than oozing, which could also

Confidential Page 56 of 86

come from a small artery or vein, but is not massive, pulsatile, and flowing.

Severe Bleeding (excluded by this protocol):

Bleeding (arterial, venous, or mixed) that is rapidly flowing, pulsatile, or spurting, which in the surgeon's judgment requires rapid control to prevent hemodynamic consequences (e.g. hypovolemia, tachycardia, or hypotension) and could involve major volume loss which if not treated rapidly, could be life threatening. SURGICEL Powder and SURGICEL Original should not be used in place of sutures or other forms of mechanical ligation for the treatment of major arterial or venous bleeding or major defects in arteries and veins.

11.4.3. Activities and Information Collected During Surgical Procedure

The following activities will be performed and the following information will be collected during the surgical procedure:

- Review of inclusion and exclusion criteria to confirm intra-operative eligibility.
 If a subject is no longer eligible, the reason for the screen failure will be documented in the source documentation and the screening log.
- Concomitant medications, as outlined in Section 11.3.5
- Hospital admission date (for overall Length of Stay)
- Entry and exit time.
- Primary surgical procedure information: open, laparoscopic, thoracoscopic. surgical specialty (general, cardiothoracic, gynecological and the type of procedure).
- Procedure time (first incision to final wound closure).
- Randomization, as outlined in Section 11.3.6.
- Assessment and determination of hemostasis at TBS
- Estimated Blood Loss (EBL)
- Transfusion information (if applicable). Amount and blood product(s) used and the type of product (e.g., red blood cells, fresh frozen plasma, platelet concentrate, etc.).
- Hemostatic methods used at the TBS prior to randomization (none, [other

Confidential Page 57 of 86

methods are impractical], suture, ligation, cautery, other.

- TBS information: Parenchyma or soft tissue type and location
- Size of TBS (length, width)
- Heparin use and time of reversal (if applicable)
- Total number of units used (SURGICEL Powder or SURGICEL Original)
- Adverse events, including any complications possibly related or related to bleeding and/or thromboembolic events.
- Drain information (if applicable)
- Surgeon Ease of Use Questionnaire—one questionnaire needs to be completed per Investigator for their first 2 cases using SURGICEL Powder (completed as soon as possible, but within approximately 72 hours).

11.4.4. Treatment Application

Upon completion of application of the randomized treatment to the TBS, the stopwatch will be immediately started, (T0) and the time on the wall clock will be recorded.

Hemostasis will be assessed at 3 minutes, 5 minutes and 10 minutes post randomized treatment application and at initiation of fascial closure for all subjects.

Refer to the IFU/IB of each product for detailed instructions on the application of SURGICEL Powder and SURGICEL Original.

11.4.5. Subjects Randomized to SURGICEL Powder

After identification of the appropriate TBS, SURGICEL Powder should be applied according to the IFU.

Confidential Page 58 of 86

03 SEP 2019, VERSION: 1.1

Key Notes from SURGICEL Powder Labelling:

- SURGICEL Powder should be applied dry so should not be moistened with water or saline prior to application. Apply an adequate amount of SURGICEL Powder by compressing the bellows, to cover the entire TBS. Depending on the bleeding intensity and anatomical location, more than one layer may be needed to achieve complete hemostasis. After SURGICEL Powder application to the TBS, the surgeon may apply pressure over the treatment site, as needed. Use of non-adhering substrate to apply pressure may prevent adhesion of the formed clot to the surgical glove or surgical instrumentation.
- SURGICEL Powder is absorbable and may be left in situ, it is advisable to remove excess powder with irrigation and aspiration once hemostasis is achieved, without disturbing the clot.
- In the event of continued bleeding or re-bleeding at the TBS at any time prior to closure, the surgeon may add additional SURGICEL Powder, if clinically appropriate, or revert to their institutional standard of care.
- If the surgeon feels re-bleeding is due to insufficient coverage of the bleeding area, additional SURGICEL Powder may be applied.

11.4.6. Subjects Randomized to SURGICEL Original

After identification of the appropriate TBS, SURGICEL Original should be applied according to its labelled instructions.

11.4.7. Hemostasis Assessments

All hemostasis assessments at the TBS will be assessed the same regardless of randomization.

Table 2: Hemostasis Assessment (Time Table)

T ₀	Start time. When randomized treatment application is complete (entire TBS covered)
T ₃	TBS Bleeding assessment 3 minutes following T ₀
T ₅	TBS Bleeding assessment 5 minutes following T ₀
T ₁₀	TBS Bleeding assessment 10 minutes following T ₀
T _F	TBS bleeding assessment post the 10-minute assessment, immediately prior to the initiation of final fascial closure

Confidential Page 59 of 86

11.4.8. Time to Hemostasis Assessment:

- The Investigator is required to call out once he/she has completed application of the product (defined as adequate coverage including additional layer, if needed) at the same time, the stopwatch must be started and the wall clock recorded by study personnel (T_0) .
- The TBS will be assessed at the time points 3 minutes (T_3) , 5 minutes (T_5) , and 10 minutes (T_{10}) following application for assessment of hemostasis.
- The Investigator must evaluate for hemostasis at the TBS immediately prior to the initiation of final fascial closure (last time TBS is visible to confirm hemostasis, T_F).
- Hemostasis will be defined as no detectable bleeding from the TBS.
- In the event of continued bleeding or re-bleeding at the TBS at any time prior to closure, the surgeon may add additional randomized treatment, if clinically appropriate, or revert to their institutional standard of care. Information on the treatment methods of re-bleeding/continuous bleeding at the TBS must be recorded.

11.4.9. Success/Failure Assessment for the Binary Primary and Secondary Effectiveness Endpoints

- During the 10-minute assessment period and following the initial application of the randomized treatment, the surgeon may reapply randomized treatment. The subject will be considered a failure for preceding binary primary and secondary effectiveness endpoints [e.g. if subjects achieve hemostasis at 3 minutes and re-bleeding occurs at 6 minutes, then the subject will be considered a failure for the preceding effectiveness endpoints (at 3 and 5 minutes)].
- Reapplication of the randomized treatment does not have an impact on the success/failure evaluation of subsequent binary effectiveness endpoints (e.g. if hemostasis is achieved by reapplication of randomized treatment, the subsequent binary endpoints will not be impacted. If an additional randomized product is applied to the TBS and the TBS is hemostatic at the 10-minute assessment period and maintained up until final fascial closure, the subject will be considered a success for the effectiveness 10-minute endpoint).
- If during the 10-minute assessment period the TBS requires further hemostatic measures (other than additional application of randomized treatment), the surgeon should perform these measures, and the subject will be considered a

Confidential Page 60 of 86

failure for all binary primary and secondary effectiveness endpoints (at 3, 5, and 10 minutes).

• Any intra-operative bleeding or any hemostatic measures at the TBS after 10 minutes and prior to initiation of final fascial closure will be considered a failure for all binary primary and secondary effectiveness endpoints.

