10.1.4. Trial Endpoints

Primary Effectiveness Endpoint

 Proportion of subjects achieving hemostatic success at 5 minutes following the application of SURGICEL Powder or SURGICEL Original with no re-bleeding requiring additional treatment at the TBS any time prior to initiation of final fascial closure.

Secondary Effectiveness Endpoints

Confidential Page 43 of 86

- Proportion of subjects achieving hemostatic success at 3 minutes following the
 application of SURGICEL Powder or SURGICEL Original with no re-bleeding
 requiring additional treatment at the TBS any time prior to initiation of final
 fascial closure.
- Proportion of subjects achieving hemostatic success at 10 minutes following the application of SURGICEL Powder or SURGICEL Original with no re-bleeding requiring additional treatment at the TBS any time prior to initiation of final fascial closure.

Safety Endpoints

- Incidence of thromboembolic events that were assessed as possibly related or related to the study treatment (from enrollment through the 30-day follow-up phone call or office visit);
- Incidence of post-operative re-bleeding that was assessed as possibly related or related to the TBS and requiring medical/surgical intervention (from initiation of final fascial closure through the 30-day follow-up phone call or office visit);
- Incidence of SAEs requiring surgical intervention and assessed as possibly related or related to the study treatment (from enrollment through the 6-month follow-up phone call or office visit)

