13. EFFECTIVENESS OUTCOMES

13.1. PRIMARY EFFECTIVENESS ENDPOINT

The primary effectiveness endpoint is defined as the proportion of subjects achieving hemostatic success at 5 minutes following the application of SURGICEL Powder or SURGICEL Original with no

re-bleeding requiring additional treatment at the TBS any time prior to initiation of final fascial closure.

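### Untreated bleeding at the target site after 10 minutes is a primary-endpoint success under the endpoint definition and a failure under Protocol 11.4.9, and the SAP does not say which rule governs.

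*Protocol*

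**What the plan says.** **Endpoint definition.** Protocol 10.1.4 defines success at 5 minutes "with no re-bleeding requiring additional treatment at the TBS any time prior to initiation of final fascial closure". Protocol 13.2 and SAP 13.1 repeat this, and the 3- and 10-minute secondary endpoints use the same condition.

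**Scoring rules.** Protocol 11.4.9 has four bullets on success and failure. The fourth fails all binary endpoints for "Any intra-operative bleeding or any hemostatic measures at the TBS after 10 minutes and prior to initiation of final fascial closure". It sets no treatment condition. The first bullet covers the 10-minute assessment period. It opens by saying that "following the initial application of the randomized treatment, the surgeon may reapply randomized treatment", and its example reads "if subjects achieve hemostasis at 3 minutes and re-bleeding occurs at 6 minutes, then the subject will be considered a failure" for the 3- and 5-minute endpoints. The example does not mention treatment.

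**Observation and discretion.** Protocol 11.4.8 states: "Hemostasis will be defined as no detectable bleeding from the TBS". Readings are scheduled at 3, 5 and 10 minutes and immediately before final fascial closure (T_F) in all subjects. If bleeding continues or recurs, "the surgeon may add additional randomized treatment, if clinically appropriate, or revert to their institutional standard of care". Protocol 11.3.6 accepts that the investigator cannot be blinded, and 10.1.12 makes the investigator the outcome assessor.

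**SAP.** SAP 13.1 gives the endpoint sentence and no derivation rule. SAP 6.3 points generally to Protocol section 11 under windowing. The list of changes in SAP 14.7 does not mention 11.4.9.

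**The concern.** Take a subject who is dry at 5 and 10 minutes, shows an ooze at T_F, and has nothing further done. A programmer working from SAP 13.1 would score a success, and one working from 11.4.9 would score a failure. This is the endpoint on which non-inferiority is decided, and the superiority step uses the same counts.

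The difference also matters for bias. No document defines when re-bleeding *requires* treatment. If that is read as the surgeon's decision, the same visible bleed becomes a success or a failure according to whether someone who knows the arm acts on it. A greater readiness to watch an ooze in one arm would raise that arm's success rate with no difference in hemostasis.

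**Working it through.** **1. The rules side by side, for a subject hemostatic at 5 minutes**

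| Later event at the target site | Endpoint definition / SAP 13.1 | Protocol 11.4.9 |
|---|---|---|
| Re-bleeding after 10 min, treated | Failure | Failure (4th bullet) |
| Bleeding after 10 min, not treated | Success, if *requiring* means the surgeon's decision | Failure (4th bullet) |
| Measure after 10 min without bleeding | Success | Failure (4th bullet) |
| Bleeding between 5 and 10 min (including at T10), not treated | Success, on the same reading | Unclear: the 6-minute example names only re-bleeding, but its bullet is about reapplication |

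The firm contradiction on untreated bleeding is row 2. Row 4 is an ambiguity.

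**2. Inputs and the plan's own figure**

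Protocol 13.2 to 13.4 give: margin 0.10, one-sided 0.025, assumed rates 0.85 (Powder) and 0.80 (Original), 80% power, 105 evaluable per arm.

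Farrington-Manning statistic:

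z = (pT − pC + 0.10) / √{[qT(1−qT) + qC(1−qC)]/n}

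Here qT and qC are the maximum-likelihood rates restricted to qT − qC = −0.10. The lower limit is the difference d at which the same statistic, with d in place of −0.10, equals 1.960.

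At 0.85 v 0.80 the restricted rates are 0.760 and 0.860, with variance sum 0.3032. The unrestricted sum is 0.85×0.15 + 0.80×0.20 = 0.2875.

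n = [(1.960√0.3032 + 0.842√0.2875)/0.15]² = 104.1, so 105 per arm.

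105/0.90 = 116.7, so 117 per arm and 234 in all. The stated sizes reproduce. Exact binomial power of the test at 105 per arm is 81.3%.

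**3. How many subjects matter**

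Planned successes are 0.85×105 ≈ 89 and 0.80×105 = 84. One subject is 1/105 = 0.95 percentage points.

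| Powder v Original | z at −0.10 | Lower limit | Non-inferior |
|---|---|---|---|
| 89 v 84 | 2.742 | −0.0566 | Yes |
| 85 v 84 | 1.980 | −0.0989 | Yes |
| 84 v 84 | 1.796 | −0.1093 | No |

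Near the boundary, one reclassified Powder subject changes the conclusion. From the planned result it takes five Powder subjects (89 − 84) and no Original subjects.

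**4. Error rate if the endpoint wording is applied**

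Set the 11.4.9 success rates at the null, 70% v 80%. Let x (Powder) and y (Original) be the further fractions whose only failing is untreated late bleeding. Under the endpoint wording the rates become 0.70 + x and 0.80 + y. The probability of declaring non-inferiority is the sum of Bin(i; 105, 0.70+x) × Bin(j; 105, 0.80+y) over all outcomes with z > 1.960. The values of x and y are assumptions.

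| x v y | Rates tested | Chance of declaring non-inferiority |
|---|---|---|
| 0% v 0% | 0.70 v 0.80 | 2.5% |
| 2% v 2% | 0.72 v 0.82 | 2.5% |
| 3% v 2% | 0.73 v 0.82 | 3.7% |
| 5% v 3% | 0.75 v 0.83 | 5.4% |
| 3% v 0% | 0.73 v 0.80 | 7.5% |
| 5% v 0% | 0.75 v 0.80 | 13.8% |

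The only re-bleeding figure in the documents is 6.6% (Protocol section 7). It is for the control product, with neither timing nor treatment stated, so it cannot fix x or y.

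**The case against.** **11.4.9 may already govern.** Its title says that it assesses success and failure for these endpoints. The SAP is based on protocol version 1.1 and withdraws nothing in 11.4.9. A specific derivation rule can reasonably be read as controlling a summary definition, and *requiring* treatment is not the same word as *receiving* it. This stands in part: the SAP has not adopted a competing rule. But neither document states precedence, and the SAP's endpoint text, taken alone, scores the subject differently.

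**The window is narrower than it looks.** A reader might infer that 11.4.9 fails any untreated bleeding after 5 minutes. It does not say so. The fourth bullet starts after 10 minutes, and the 6-minute example can be read as a case of reapplication. This objection stands.

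**11.4.9 does not remove discretion.** A reader might infer that under 11.4.9 the bleeding alone decides. But a discretionary measure after 10 minutes also fails the subject, and the same unblinded investigator judges whether bleeding is detectable. Scoring on observed bleeding moves part of the discretion from treating to seeing and recording. This stands too.

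**Large effects need a one-sided pattern.** The 7.5% and 13.8% figures require untreated bleeding in Powder and none in Original. Nothing in the documents shows differential behavior. T_F is also the last view of the site, so closing over visible bleeding is plausibly uncommon.

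**Conclusion.** For bleeding after 10 minutes and before closure that is not treated, the documents give two scores for the primary endpoint and no order of precedence. That holds on the text, provided *requiring* is read as the surgeon's decision; no other criterion is given. For untreated bleeding between 5 and 10 minutes, 11.4.9 is ambiguous and not contradictory.

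The sample size is unaffected. The conclusion could turn on one subject near the margin, and on five in one arm only at the planned rates. Under the assumed frequencies the error runs from 2.5% (equal in both arms) through 3.7% and 5.4% (modest imbalance) to 13.8% (5% in Powder only). The documents do not support treating the upper figures as the trial's expected error: they give no frequency of untreated bleeding and no sign of imbalance. The point is a scoring rule that should be settled in writing. It is not evidence that the result is biased.

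**What to change.** 1. In SAP 13.1 and 13.2, state that success and failure are derived by Protocol 11.4.9. Detectable bleeding at the target site after 10 minutes and before closure, including at T_F, is then a failure for all binary endpoints whether or not it was treated. Align the wording of Protocol 10.1.4 and 13.2.
2. State how untreated bleeding between 5 and 10 minutes, including at T10, is scored for the 3- and 5-minute endpoints. Scoring it as failure would be consistent with the fourth bullet, but it extends that bullet and should be labeled as a decision.
3. Report the scoring conditional on additional treatment as a sensitivity analysis.

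**Cost.** Wording and one table. T10 and T_F are already read in every subject; bleeding seen only between those readings counts only if it is noted. Success rates may fall slightly. If 3% of successes in each arm are reclassified, the rates become 0.85×0.97 = 0.8245 and 0.80×0.97 = 0.776, and exact power falls from 81.3% to 76.5%. Some dependence on the unblinded investigator's judgment remains. The change concerns outcome scoring only, not whether the surgeon should treat.

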11.5. Post-Surgery until Hospital Discharge

Prior to discharge, the following data will be recorded:

- Changes in concomitant medications.
- Was drain used, if yes record days, quantity and describe content (type of the discharge, e.g. serosal fluid, blood, etc.).
- Physical examination (vital signs: BT, BP, HR and RR) for 3 consecutive days or until hospital discharge, whichever comes first.
- CBC with Hgb test prior to discharge.
- Adverse events, including reoperation, any complications possibly related to bleeding and/or thromboembolic events.
- Date of hospital discharge (for overall Length of Stay).

11.6. 30-day Follow-Up Phone call or Office Visit (+ 14 days)

The following information will be recorded at the clinical follow-up phone call or office visit approximately 30 days following the study surgery:

- Changes in concomitant medications, including use of any blood products following hospital discharge.
- Adverse events, including any reoperations and/or complications possibly related or related to bleeding and/or thromboembolic events.

11.7. Six-Month Follow-Up Phone Call or Office Visit (+/- 30 days)

• All enrolled subjects will receive a 6-month (+/-30 days) follow-up phone call or office visit to assess the occurrence of any SAEs requiring surgical intervention and assessed as possibly related or related to the study treatment.

Confidential Page 61 of 86

All SAEs that were ongoing at the 30-day post-surgery visit will be followed until
completion of the 6-month follow-up phone call or office visit, or until a stable
resolution, whichever comes first.

12. MONITORING PLAN

This study is performed according to the Good Clinical Practice for Medical Product Trials and related laws and regulations.

The Sponsor bears the monitoring responsibility for the clinical trial and will select the qualified monitor to execute the monitoring responsibility.

The monitor should comply with the related laws and regulations and the standard operating procedure established by the Sponsor with regard to the monitoring to monitor each phase of this study.

The monitor should contact and visit the investigators at a regular basis and make the field visit/monitoring for the study. The monitor should make a visit when the first subject is enrolled, and make a necessary visit at a regular basis (about every 4 or 6 weeks) during the study period.

The monitoring includes the visit to clinical trial institution, verification of CRF data, communication with investigators and clinical trial institution, ensuring that this study will be performed strictly in compliance with the trial protocol and the requirements of regulations of Good Clinical Practice, etc.

The on-site inspection of CRF includes verifying the source document and checking whether original data is true, accurate, complete and clear, the original document of each subject is complete.

This study may be subject to the audit by the Sponsor or regulatory authority. If such audit is performed, the Investigator must agree the auditor to look up the records of subjects. The Investigator agrees the Sponsor or its appointed representative and regulatory authority to monitor all project-related study documents on site by signing on the signature page of this trial protocol.

